### **3.1 Rationale for Dosage Selection**

The pacritinib  $IC_{50}$  for the therapeutic targets is as follows:

- JAK2: 6 nM
- IRAK-1: 13.6 nM
- CSF-1R: 39.5 nM

Inhibition of these targets is thought to mediate the cytokine storm and development of acute respiratory distress syndrome seen in patients with COVID-19. The goal of dose selection in this study is to rapidly achieve many-fold higher free pacritinib plasma concentrations than the  $IC_{50}$ . Following oral administration of 200 mg BID and 400 mg QD, free plasma drug concentration observed is about 200 nM and 250 nM, respectively. As COVID-19 is a rapidly progressing disease with significant cytokine storm, the treatment goal should be rapid control of cytokine storm; hence, the dosage regimen that provides rapid plasma concentration many folds higher than  $IC_{50}$  is desired. Therefore, dosing 400 mg QD on Day 1 followed by 200 mg BID provides steady-state equivalent plasma concentration on Day 1, which is similar to the steady-state concentration seen with 200 mg BID ([Figure 1](#)).

**Figure 1 Simulated Median Concentration-Time Course in Myelofibrosis Patients (Day 1 to Day 8)**

Abbreviations: BID = twice daily; QD = once daily.

Based on all available data from pre-clinical studies to clinical data in both healthy subjects and patients with hematologic malignancies including myelofibrosis, pacritinib 400 mg QD on Day 1 followed by 200 mg BID dosing starting on Day 2 has been selected as the dosing for the PRE-VENT study.

## 4 PATIENT SELECTION AND WITHDRAWAL

### 4.1 Target Population

#### 4.1.1 *Inclusion Criteria*

1. Hospitalized or will be hospitalized prior to randomization for the treatment of severe COVID-19 with SARS-CoV-2 infection confirmed by either a) a positive reverse transcriptase polymerase chain reaction (RT-PCR) or b) an antigen-based test from any respiratory, nasopharyngeal, saliva, blood, or stool specimen at Screening or documented within 1 week prior to the start of Screening (Severe COVID-19 is defined as confirmed disease in patients who are hospitalized with hypoxia [ $\text{SpO}_2 \leq 93\%$  on room air], respiratory rate  $>30$ ,  $\text{PaO}_2/\text{FiO}_2 <300$ , but do not require IMV).
2. Age  $\geq 18$  years
3. Platelet count  $\geq 50,000/\mu\text{L}$
4. If fertile, willing to use effective birth control methods during the study
5. Provision of informed consent within 96 hours after hospitalization

#### **4.1.2     *Exclusion Criteria***

1. In the opinion of the investigator, progression to death is imminent and inevitable within the next 24 hours, irrespective of the provision of treatments
2. Currently intubated or intubated between screening and randomization
3. Suspected active uncontrolled bacterial, fungal, viral, or other infection (besides COVID-19)
4. Prior allogenic hematopoietic stem cell transplantation
5. Active lung cancer or history of lung cancer within the past 12 months
6. Any active grade 2 or higher hemorrhage
7. Any active gastrointestinal or metabolic condition that could interfere with absorption of oral medication
8. Uncontrolled intercurrent illness that, in the judgment of the treating physician, would limit compliance with study requirements
9. Known seropositivity for human immunodeficiency virus with CD4 count < 200/mm^3 within 3 months prior to randomization
10. Pregnant or breastfeeding, or positive pregnancy test in a pre-dose examination
11. Concurrent enrollment in another interventional trial (investigational COVID-19 antiviral studies are permitted)
12. Serum creatinine > 2.5 mg/dL
13. Total bilirubin > 4× the upper limit of normal
14. QT corrected by the Fridericia method (QTcF) prolongation > 480 msec
15. Known history of New York Heart Association Class II, III, or IV congestive heart failure prior to hospital admission
16. Known allergic reaction to any JAK2 inhibitor
17. Exposure to any JAK2 inhibitor within 28 days
18. Currently receiving a strong CYP3A4 inhibitor or strong P450 inducer ([Appendix 1](#) and [Appendix 2](#), respectively) and unable to stop the medication prior to the first dose of study drug and throughout the duration of study drug administration
19. Treatment with cytoreductive chemotherapy administered within 14 days prior to randomization

20. Administration of an IL-1 or IL-6 blocking immunomodulatory agent (such as tocilizumab, canakinumab, sarilumab, anakinra) within 48 hours prior to randomization
21. Currently receiving therapeutic anticoagulation or anti-platelet medication and unable to stop the medication prior to randomization. Prophylactic anticoagulation therapy or aspirin ( $\leq 100$ mg) are permitted.
22. Unable to ingest capsules or tablets at randomization

#### **4.2 Withdrawal of Patients from Study**

Patients have the right to stop study participation at any time and for any reason without prejudice to his or her future medical care. Patients (or a legally acceptable representative) may decline to continue receiving pacritinib/placebo and/or other protocol-required therapies or procedures at any time during the study. Patients will be encouraged to allow continued follow-up for study procedures and safety monitoring; however, patients may withdraw consent for all study procedures or for specific study procedures. Data collected up to the date of withdrawal of consent will be included in the analysis of the study. The Investigator is to discuss with the patient the appropriate procedures for withdrawal from the study. The Investigator or Sponsor has the right to discontinue any patient from study participation.

Reasons for patient discontinuation may include, but are not limited to, the following:

- Patient's request, with or without a stated reason
- Noncompliance
- Physician's decision
- Sponsor's discretion
- Lost to follow-up

#### **5 METHOD OF TREATMENT ASSIGNMENT AND BLINDING**

Eligible patients will be centrally randomized in a 1:1 allocation ratio to receive pacritinib (400 mg QD on Day 1, then 200 mg BID from Day 2 to Day 14) + SOC or placebo + SOC according to a stratified permuted block design stratified by age (< 60 years versus  $\geq 60$  years) and the 7-point clinical status scale (baseline 3 or 4 versus 5). Assigned therapy may be given for an additional 7 days (for a total of 21 days) with the approval of the Medical Monitor if, in the opinion of the investigator, the patient's clinical signs and symptoms are improving and the potential benefit outweighs the potential risk.

This study is double-blind; the Sponsor, study patients, and Investigators will be blinded to treatment assignments. The IDMC will have access to unblinded data. Individual patient unblinding may occur at the request of the Investigators if necessary for medical reasons and to assess suspected unexpected serious adverse reactions.

## 6 STUDY TREATMENT

### 6.1 Study Treatment Administration

Patients will be supplied with blinded pacritinib 100 mg capsules or matching placebo.

**Table 2. Study Treatments**

Treatment	Dosage/Regimen
Pacritinib + SOC	400 mg (4 capsules) QD on Day 1, then 200 mg (2 capsules) BID from Day 2 to Day 14 + SOC. Pacritinib/placebo is administered orally or via oro/nasogastric tube. Assigned therapy may be given for an additional 7 days (for a total of 21 days) with the approval of the Medical Monitor if, in the opinion of the investigator, the patient's clinical signs and symptoms are improving and the potential benefit outweighs the potential risk.
Placebo + SOC	4 capsules QD on Day 1, then 2 capsules BID from Day 2 to Day 14 + SOC. Pacritinib/placebo is administered orally or via oro/nasogastric tube. Assigned therapy may be given for an additional 7 days (for a total of 21 days) with the approval of the Medical Monitor if, in the opinion of the investigator, the patient's clinical signs and symptoms are improving and the potential benefit outweighs the potential risk.

Abbreviations: BID = twice daily; QD = once daily; SOC = standard of care.

### 6.2 Study Treatment Description and Storage

#### 6.2.1 *Pacritinib*

Pacritinib for oral or oro/nasogastric tube administration is supplied in capsules containing 100 mg (as the free base) in body size 0, red cap/gray opaque hard gelatin capsules. The inactive ingredients are microcrystalline cellulose, magnesium stearate, and polyethylene glycol 8000.

Each capsule contains 146 mg of pacritinib citrate, which is equivalent to 100 mg pacritinib free base.

Direct contact of the powder in pacritinib capsules with the skin or mucous membranes should be avoided. If such contact occurs, affected areas should be washed thoroughly with water.

Pacritinib capsules should be stored at controlled room temperature 20°C to 25°C or 68°F to 77°F, with excursions allowed from 15°C to 30°C or 59°F to 86°F. All pacritinib supplies must be kept in a restricted access area.

#### 6.2.2 *Placebo*

Placebo for oral or oro/nasogastric tube administration will be supplied as capsules that match the pacritinib 100 mg capsules in appearance.

The excipients, container, handling instructions, and storage conditions are the same as those described for the pacritinib capsules (Section 6.2.1).

### **6.3 Dosage, Route, and Mode of Administration**

Patients will take 4 capsules of pacritinib/placebo at one time on Day 1 and two capsules BID from Day 2 to Day 14. Assigned therapy may be given for an additional 7 days (for a total of 21 days) with the approval of the Medical Monitor if, in the opinion of the investigator, the patient's clinical signs and symptoms are improving and the potential benefit outweighs the potential risk. Pacritinib/placebo will be taken orally or via oro/nasogastric tube at the same time of day, with or without food.

Any missed or vomited doses should not be retaken or replaced.

### **6.4 Drug Accountability**

At the Day 15 or EOT assessment, any unused pacritinib/placebo capsules will be returned to the pharmacy. Compliance with pacritinib/placebo will be reported by the site as the number of missed doses.

### **6.5 Pacritinib Treatment Adjustments for Adverse Events**

#### **6.5.1 *Treatment Interruption and Discontinuation***

Safety parameters including AEs, complete blood count (CBC) with differential, serum chemistry, and ECGs will be assessed according to protocol.

Pacritinib/placebo should be interrupted in the setting of certain AEs described below. Where possible, pacritinib/placebo should be held if an invasive procedure, including central venous catheter insertion, is performed; drug should be restarted after 24 hours without signs or symptoms of active bleeding. Pacritinib/placebo may also be held at the discretion of the investigator. The Medical Monitor should be notified of all such drug holds.

Pacritinib/placebo should be discontinued in the setting of intolerable AEs described below, or if the patient withdraws consent to continue pacritinib/placebo. Pacritinib/placebo may also be discontinued at the discretion of the investigator; the Medical Monitor should be notified of all such drug discontinuations.

#### **6.5.2 *Dosage Management Guidelines for Adverse Events***

In prior studies, pacritinib has been associated with diarrhea, nausea, anemia, thrombocytopenia, QTc prolongation (generally mild), and risk of bleeding. Safety assessments will include hematologic parameters (CBC with differential), assessment of organ function (serum chemistry), monitoring for QTc prolongation, and general AE monitoring.

Patients who develop worsening gastrointestinal symptoms with the initiation of pacritinib/placebo treatment may be treated with standard antidiarrheal and/or anti-emetic medications.

Patients receiving study drug may also receive treatment-dose anticoagulants or anti-platelet agents, if required; patients do not need to discontinue study drug if one of these medications is

initiated. However, patients should not receive such agents concomitant with study drug administration if their platelet counts drop to  $< 50,000/\mu\text{L}$ ; prophylaxis-dose anticoagulants are permitted for all patients on study. Treatment-dose anticoagulants and anti-platelet agents may be administered at any dose after the study drug treatment period has ended.

Additional dose modifications for treatment-related AEs are described in this section. Dose modifications for any instance of QTcF prolongation (irrespective of relationship to study drug) are also described in this section. AEs are deemed treatment-related if they are considered possibly related to pacritinib/placebo; AEs that are considered unlikely related to pacritinib/placebo do not require dose modification. Dose levels referenced in the following tables refer to the following available doses: 200 mg BID, 100 mg BID, and 100 mg QD.

Patients who require dose reduction may not subsequently re-escalate the dose.

### **6.5.3 Dosage Management Guidelines for Bleeding and Thrombocytopenia**

Hematology parameters, including CBC (which includes white blood cell [WBC] count, differential, hemoglobin count, hematocrit, and platelet count), will be evaluated for inpatients during the study. These parameters should be monitored more frequently if clinically required.

[Table 3](#) indicates the required dose interruptions and modifications for treatment-related bleeding and thrombocytopenia. Of note, if more than one toxicity is experienced simultaneously, the higher-grade toxicity should determine the dose interruption/modification.

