**Table 3. Treatment-Related Thrombocytopenia and Bleeding**

Event	CTCAE (v4.03) Grade	Management/Action
Thrombocytopenia	2  (Management required only for patients starting with normal platelet counts; patients starting with grade 1 or 2 thrombocytopenia at Baseline do not require dose adjustments)	

Reduce to 50% of the prior dose

	3  (Management required only for patients starting with normal platelet count or grade 1 thrombocytopenia; patients starting with grade 2 or 3 thrombocytopenia at Baseline do not require dose adjustments)	

Hold pacritinib/placebo. If the toxicity resolves to Baseline grade within 7 days, treatment may be resumed at the same level or at 50% of the dose. If the toxicity does not resolve or if it occurs at the lowest dose level, pacritinib/placebo must be discontinued.

If criterion is met on the day of hospital discharge, pacritinib/placebo should not be administered as an outpatient.

	4  (Management required only for patients starting with normal platelet count or grade	

Hold pacritinib/placebo. If the toxicity resolves to Baseline grade within 7 days, treatment may be resumed at the same level or at 50% of the dose. If the toxicity does not resolve

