**Table 3. Treatment-Related Thrombocytopenia and Bleeding**

Event	CTCAE (v4.03) Grade	Management/Action
	1 or 2 thrombocytopenia; patients starting with grade 3 or 4 thrombocytopenia at Baseline do not require dose adjustments)	or if it occurs at the lowest dose level, pacritinib/placebo must be discontinued. 

• If criterion is met on the day of hospital discharge, pacritinib/placebo should not be administered as an outpatient.

Bleeding	1	

• No change

	2	

• Hold pacritinib/placebo until bleeding resolves for up to 2 days. Restart pacritinib/placebo at the same dose. If bleeding recurs, hold again for up to 2 days and restart at 50% of the prior dose.

• If bleeding is ongoing after 2 days, discontinue pacritinib/placebo.

• If treatment-related bleeding grade 2 or higher occurred on study, pacritinib/placebo should not be administered as an outpatient.

	3	

• Hold pacritinib/placebo until bleeding resolves for up to 2 days. Restart pacritinib/placebo at 50% of the prior dose. If bleeding recurs, hold again for up to 2 days and restart at 50% of the prior dose.

• If bleeding is ongoing after 2 days, discontinue pacritinib/placebo.

• If treatment-related bleeding grade 2 or higher occurred on study, pacritinib/placebo should not be administered as an outpatient.

	4	

• Discontinue pacritinib/placebo.

Abbreviations: CTCAE = Common Terminology Criteria for Adverse Events.

Dose interruptions and modifications for SOC agents will be based on the prescribing information described in the most current versions of the agents' approved labeling.

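### The higher-grade rule in Protocol 6.5.3 permits a full-dose restart after grade 3 bleeding when grade 4 thrombocytopenia is also present, although the bleeding row requires half dose

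*Protocol*

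**What the plan says.** Protocol 6.5.3 introduces Table 3 as mandatory: it "indicates the required dose interruptions and modifications for treatment-related bleeding and thrombocytopenia". It then adds a rule for events that occur together: "if more than one toxicity is experienced simultaneously, the higher-grade toxicity should determine the dose interruption/modification".

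The Table 3 rows that matter here are:

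- **Thrombocytopenia, grades 3 and 4** (same resumption text in both rows): hold, then "If the toxicity resolves to Baseline grade within 7 days, treatment may be resumed at the same level or at 50% of the dose". Discontinue if it does not resolve or if it occurs at the lowest dose level. The grade 4 row applies to patients whose Baseline platelets were normal or grade 1 to 2.
- **Bleeding, grade 3**: hold for up to 2 days, then "Restart pacritinib/placebo at 50% of the prior dose".
- **Bleeding, grades 2 and 3**: "If bleeding is ongoing after 2 days, discontinue pacritinib/placebo". Also, "If treatment-related bleeding grade 2 or higher occurred on study, pacritinib/placebo should not be administered as an outpatient".

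Section 6.5.2 limits these actions to treatment-related events ("AEs that are considered unlikely related to pacritinib/placebo do not require dose modification") and makes any reduction permanent: "Patients who require dose reduction may not subsequently re-escalate the dose". Nothing in 6.5.1 to 6.5.3 says that the stricter of two rows prevails.

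**The concern.** The sentence in 6.5.3 assumes that a higher grade always carries a stricter action. Within Table 3 that fails. The grade 4 thrombocytopenia row leaves the restart dose open, while the grade 3 bleeding row fixes it at half. If the higher grade decides, a patient who has bled at grade 3 may go back to full dose because the platelets were also very low. The same bleed without thrombocytopenia would require half dose for the rest of the course.

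Bleeding with low platelets is the combination that this section exists to manage, and 6.5.2 lists both thrombocytopenia and bleeding among the known pacritinib risks. At stake are the safety of a small number of inpatients and consistency between sites: one site may follow the deciding row alone and another may apply both rows to the same event.

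**Working it through.** **Inputs.** Table 3 gives actions for thrombocytopenia grades 2 to 4 (T2 to T4) and bleeding grades 1 to 4 (B1 to B4). The dose levels in 6.5.2 are 200 mg BID, 100 mg BID and 100 mg QD. There is no planned figure to reproduce, so the check is to apply the rule to every pair of grades, counting a first occurrence of each event.

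**Step 1: all pairs.** 3 × 4 = 12 pairs, of which thrombocytopenia is higher in 6, the grades are equal in 3, and bleeding is higher in 3.

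| Pairs | Row that decides | Effect of the rule |
|---|---|---|
| T2/B1, T3/B1, T4/B1 | Thrombocytopenia | B1 needs no change; nothing is lost |
| T3/B2, T4/B2 | Thrombocytopenia | Restart dose: nothing lost, because B2 restarts at the same dose. 2-day stop: unclear |
| T4/B3 | Thrombocytopenia | Half-dose restart becomes optional. 2-day stop: unclear |
| T2/B2, T3/B3, T4/B4 | None named | Rows differ; the rule is silent |
| T2/B3, T2/B4, T3/B4 | Bleeding | The bleeding row is at least as strict; nothing is lost |

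**Step 2: the restart dose at T4/B3.** The permitted fractions of the prior dose are {100%, 50%} under the deciding T4 row and {50%} under the B3 row. Applying both rows leaves {50%}. The rule therefore allows 100%, which the bleeding row does not. This is the only one of the 12 pairs in which that happens.

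**Step 3: the 2-day stop at T3/B2, T4/B2 and T4/B3.** The stop sits in the row that does not decide. Whether it gives way depends on whether the words interruption/modification in the rule include discontinuation. The text points both ways (see the objection), so the position is unclear.

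**Step 4: equal grades.** At T2/B2 one row halves the dose and the other holds and restarts at the same dose. At T3/B3 the rows are {100%, 50%} and {50%}. At T4/B4 one row holds with possible resumption and the other discontinues. No row is named as deciding.

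**Step 5: size at T4/B3, as an illustration.** Assumptions: starting dose 200 mg BID (400 mg/day); both events begin on Day 4; bleeding stops on Day 6, within the 2 days; platelets reach Baseline grade on Day 9, within the 7 days; the patient stays in hospital; treatment ends on Day 14 without the optional extension. Days 9 to 14 are 6 days.

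- Permitted by the rule: 6 × 400 = 2,400 mg.
- Both rows applied: 6 × 200 = 1,200 mg.
- Permitted excess: 2,400 − 1,200 = 1,200 mg, that is, twice the dose.

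The comparator has to be both rows together. A restart on Day 6 under the bleeding row alone is not available, because the T4 row still requires a hold until the platelets recover.

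**The case against.** The strongest reply is that the T4 row grants a permission and gives no contrary instruction. A half-dose restart after platelet recovery satisfies both rows, no site is forced to breach either, and under 6.5.1 the investigator may hold or stop at discretion and the Medical Monitor should be told of such holds. This stands as a limit on the harm. It does not remove the defect: Table 3 makes the half-dose restart a requirement, and the rule turns it into a choice.

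A second reply is that in the illustration the events overlap only on Days 4 to 6, when both rows say hold, so the half-dose term could revive once the overlap ends. The text does not say so. The rule lets the higher grade determine the modification, and the restart dose is part of that modification. If bleeding and platelets recovered together within 2 days, the restart decision would fall directly at the end of the overlap and the conflict would be immediate.

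A third reply is rarity. Both events must be treatment-related, Baseline platelets normal or grade 1 to 2, the dose above the lowest level, platelets back to Baseline grade within 7 days, and the investigator must choose full dose. The outpatient bar is triggered by the occurrence of grade 2 or higher bleeding and so probably still applies, which confines the exposure to inpatients. All of this stands.

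A reader might infer something stronger: that the rule also overrides the 2-day bleeding stop, so that full dose is permitted where no drug should be given. The argument for it is that 6.5.3 describes the whole of Table 3 as interruptions and modifications, and the table contains discontinuations. Against it, 6.5.1 treats interruption and discontinuation separately, with different triggers, and 8.1.3.4 codes interruption and withdrawal as different actions. The documents therefore support calling the stop's status unclear, and no more.

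**Conclusion.** The sentence in 6.5.3 is wrong as written; severity is minor. For grade 4 thrombocytopenia with grade 3 bleeding it permits a full-dose restart that the bleeding row excludes. Under the illustrative timings this is up to 2,400 mg against 1,200 mg over Days 9 to 14. These timings were chosen to show the mechanism and do not come from the protocol. The counts of grade pairs describe the table and are not risks.

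The documents give no frequency for the two events together, and it is probably low. The nearest figure is for grade 3 bleeding alone at 200 mg BID in PAC203: 3 of 54 (5.6%), with no grade 4 events, in myelofibrosis over a median of 21 weeks. It is context and does not estimate the joint event in this trial.

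Two lesser gaps belong to the same sentence: the unclear status of the 2-day stop in three pairs, and the lack of a deciding row in the three equal-grade pairs. There is no effect on the primary efficacy result.

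**What to change.** Replace the sentence in 6.5.3 with: *When more than one toxicity is present at the same time, including at equal grades, apply the most restrictive action required by any applicable row, including discontinuation.*

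For T4/B3 this leaves only the half-dose restart after both events have resolved in time. It makes the 2-day stop explicit in T3/B2, T4/B2 and T4/B3, and it settles the equal-grade pairs. Whether grade 3 or 4 thrombocytopenia on its own should allow resumption at full dose is a medical choice that this change leaves alone.

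The cost is one sentence in the next amendment or in a dose-management clarification letter. It needs no new assessments and no change to the analysis.
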